2.2 FURTHER OBJECTIVES AND FURTHER ENDPOINTS

2.2.1 Further objectives

2.2.2 Further endpoints

3. DESCRIPTION OF DESIGN AND TRIAL POPULATION

3.1 OVERALL STUDY DESIGN AND PLAN

This is a US / Europe, multi-center observational study with an enrollment target of 50 patients with GA secondary to AMD who are not receiving treatment for GA.

The observational period is dependent on the potential future availability of approved treatments for GA; in the absence of an approved therapy, this observational study may extend to 12 months. Visual function and anatomic measures will be collected at baseline, 3 months, 6 months, and 12 months. The study will consist of a screening period of up to 28 days (Days -28 to -1) and an observation period of maximally 12 months.

Enrolled patients must satisfy all eligibility criteria at both the screening period and the Day 1 visit. As part of the screening process, the Central Reading Center (CRC) will evaluate color fundus photographs, FAF images, to provide an objective assessment of patient eligibility. Patients must also meet BCVA and other eligibility criteria. Screen-failed patients can rescreen up to two additional times to qualify for study participation. One eye will be chosen as the study eye. If both eyes are eligible, the eye with the better visual function (as determined by the investigator and the patient) will be the study eye; if both eyes have the same visual function, the eye with the larger area of GA will be selected as the study eye (data will be collected on both eyes but analysed for the study eye only).

3.2 SELECTION OF STUDY POPULATION

Screening of patients for this study is competitive, i.e. screening for the study will stop at all sites at the same time once a sufficient number of patients has been screened. Investigators will be notified about screening completion and will then not be allowed to screen additional patients for this study.

3.2.1 Main diagnosis for study entry

Patients with GA secondary to AMD who are not receiving treatment for GA and have not previously receiving active treatment in clinical trials in the indication under investigation will be enrolled and followed for up to 12 months. Please refer to [section 8.3.1](#) (Source Documents) for the documentation requirements pertaining to the in- and exclusion criteria.

3.2.2 Inclusion criteria

1. Signed and dated written informed consent in accordance with ICH-GCP and local legislation prior to admission to the study
2. Age ≥ 60 years
3. Ability (including a sufficient general health status according to investigators judgement) and willingness to undertake all scheduled visits and assessments including predefined methodology and standards utilizing microperimetry

4. GA secondary to AMD with no evidence of prior or active choroidal neovascularization (CNV) in the study eye
5. GA lesion in the study eye must reside completely within the FAF imaging field (Field 2-30 degree image centered on the fovea)
6. BCVA of 20/63 or better (Snellen equivalent) using ETDRS charts at starting distance of 4 m in the study eye
7. Well demarcated area(s) of GA secondary to AMD with no evidence of prior or active CNV in the study eye
 - The total GA lesion size $\geq 1.2 \text{ mm}^2$ (approximately ≥ 0.5 disc area [DA]) and $\leq 17.78 \text{ mm}^2$ (approximately ≤ 7 DA) and must reside completely within the FAF imaging field (Field 2–30 degree image centered on the fovea)
 - If GA is multifocal, at least 1 focal lesion must be $\geq 1.2 \text{ mm}^2$ (approximately ≥ 0.5 DA)
8. Sufficiently clear ocular media, adequate pupillary dilation, and fixation to permit quality fundus imaging in the study eye

3.2.3 Exclusion criteria

1. GA in either eye due to causes other than AMD (for example, monogenetic macular dystrophies [e.g., Stargardt disease, cone rod dystrophy] or toxic maculopathies [e.g., chloroquine/hydroxychloroquine maculopathy])
2. Receiving active treatment in any studies of investigational drugs for GA/dry AMD in the study eye
3. Mean sensitivity difference > 3 dB between the two microperimetry examinations in the screening visit.
4. History of vitrectomy surgery, submacular surgery, or other surgical intervention for AMD in the study eye
5. Previous laser photocoagulation for CNV, diabetic macular edema, retinal vein occlusion, and proliferative diabetic retinopathy in the study eye
6. Prior treatment with Visudyne[®], external-beam radiation therapy, or transpupillary thermotherapy in the study eye
7. History of prophylactic subthreshold laser treatment for AMD in the study eye
8. Previous intravitreal drug delivery in the study eye (e.g., intravitreal corticosteroid injection, anti-angiogenic drugs, anti-complement agents, or device implantation). A single intraoperative administration of a corticosteroid during cataract surgery for cystoid macular edema prophylaxis at least 3 months prior to screening is permitted.
9. RPE tear that involves the macula in either eye
10. Any concurrent ocular or intraocular condition in the study eye (e.g., cataract or diabetic retinopathy) that, in the opinion of the investigator, could do either of the following:
 - Require medical or surgical intervention during the study period to prevent or treat vision loss that might result from that condition
 - If allowed to progress untreated, could likely contribute to loss of at least two Snellen equivalent lines of BCVA during the study period
11. Previous violation of the posterior capsule in the study eye unless it occurred as a result of Yttrium Aluminum Garnet (YAG) laser posterior capsulotomy in association with prior posterior chamber intraocular lens implantation

12. Spherical equivalent of the refractive error in the study eye demonstrating >6 diopters of myopia
13. For patients who have undergone prior refractive or cataract surgery in the study eye, the preoperative refractive error in the study eye should not have exceeded 6 diopters of myopia.
14. Intraocular surgery (including cataract surgery) in the study eye within 3 months preceding Day 1
15. History of glaucoma-filtering surgery in the study eye
16. History of corneal transplant in the study eye
17. Major surgery (major according to the investigator's assessment) performed within 12 weeks prior to randomization or planned within 12 months after screening, e.g. hip replacement
18. Previous enrolment in this study
19. Currently enrolled in another investigational device or drug trial, or less than 30 days since ending another investigational device or drug trial(s), or receiving other investigational treatment(s)

3.2.4 Withdrawal of patients from study participation

3.2.4.1 Withdrawal of consent for study participation

Patients may withdraw their consent for study participation at any time without the need to justify the decision.

This will however mean that no further information may be collected for the purpose of the study and negative implications for the scientific value may be the consequence. Furthermore it may mean that further patient follow up on safety cannot occur.

If a patient wants to withdraw consent, the investigator should explain the difference between treatment withdrawal and withdrawal of consent for study participation and explain the options for continued follow up after withdrawal from study treatment, please see [section 3.2.4.1](#) above.

3.2.4.2 Discontinuation of the study by the sponsor

Boehringer Ingelheim (BI) reserves the right to discontinue the study overall or at a particular study site at any time.

The investigator / the study site will be reimbursed for reasonable expenses incurred in case of study termination (except in case of the third reason).

4. TREATMENTS

4.1 INVESTIGATIONAL TREATMENTS

No treatments will be administered in this biomarker evaluation study.

4.2 OTHER TREATMENTS, EMERGENCY PROCEDURES, RESTRICTIONS

4.2.1 Other treatments and emergency procedures

There are no special emergency procedures to be followed.

4.2.2 Restrictions

4.2.2.1 Restrictions regarding concomitant treatment

Patients should not be included in an interventional trial for the condition under investigation while being part of this study. There are no other restrictions regarding concomitant treatment to be followed.

4.2.2.2 Restrictions on diet and life style

There are no restrictions regarding diet and lifestyle to be followed.

5. ASSESSMENTS

5.1 ASSESSMENTS OF SAFETY

5.1.1 Physical examination

NA

5.1.2 Safety laboratory parameters

No safety laboratory parameters will be determined.

5.1.3 Assessment of adverse events

5.1.3.1 Definitions of AEs

AE reporting to sponsor and timelines

This study will not use a BI Investigational Medical Product (IMP). All AEs should be collected on the appropriate Case Report Form (CRF) page only.

Adverse event

An AE is defined as any untoward medical occurrence in a patient or clinical study subject and which does not necessarily have to have a causal relationship with this study.

An AE can therefore be any unfavourable and unintended sign (including an abnormal laboratory finding), symptom, or disease temporally associated with the use of a medicinal product, whether or not considered related to the study procedures.

Serious Adverse Event (SAE)

A SAE is defined as any AE which fulfils at least one of the following criteria:

- results in death,
- is life-threatening, which refers to an event in which the patient was at risk of death at the time of the event; it does not refer to an event that hypothetically might have caused death if more severe,
- requires inpatient hospitalisation or
- requires prolongation of existing hospitalisation,
- results in persistent or significant disability or incapacity, or
- is a congenital anomaly / birth defect, or
- is deemed serious for any other reason if it is an important medical event when based on appropriate medical judgement which may jeopardise the patient and may require medical or surgical intervention to prevent one of the other outcomes listed in the above definitions.

Examples of such events are intensive treatment in an emergency room or at home for allergic bronchospasm, blood dyscrasias or convulsions that do not result in hospitalisation or development of dependency or abuse.

AEs considered “Always Serious”

Cancers of new histology and exacerbations of existing cancer must be classified as a serious event regardless of the duration between discontinuation of the drug and must be reported as described in [section 5.1.3.2](#), subsections “**AE Collection**” and “**AE reporting to sponsor and timelines**”

In accordance with the European Medicines Agency initiative on Important Medical Events, BI has set up a list of further AEs, which by their nature, can always be considered to be “serious” even though they may not have met the criteria of an SAE as defined above. The latest list of “Always Serious AEs” can be found in the electronic Data Capture (eDC) system. A copy of the latest list of “Always Serious AEs” will be provided upon request. These events should always be reported as SAEs as described above.

Adverse events of special interest (AESIs)

No AESIs have been defined for this study.

Intensity (severity) of AEs

The intensity (severity) of the AE should be judged based on the following:

- | | |
|-----------|--|
| Mild: | Awareness of sign(s) or symptom(s) that is/are easily tolerated |
| Moderate: | Sufficient discomfort to cause interference with usual activity |
| Severe: | Incapacitating or causing inability to work or to perform usual activities |

Causal relationship of AEs

Medical judgement should be used to determine the relationship, considering all relevant factors, including pattern of reaction, temporal relationship, de-challenge or re-challenge, confounding factors such as concomitant medication, concomitant diseases and relevant history.

- Yes: There is a reasonable causal relationship between a study procedure and the AE.
No: There is no reasonable causal relationship between a study procedure and the AE.

5.1.3.2 Adverse event collection and reporting

AE Collection

The investigator shall maintain and keep detailed records of all AEs in the patient files. The following must be collected and documented on the appropriate CRF(s) by the investigator:

- From signing the informed consent onwards until the individual patient’s end of study:
-all AEs (serious and non-serious).
- After the individual patient’s end of study:
the investigator does not need to actively monitor the patient for AEs but should only report related SAEs of which the investigator may become aware of by any means of communication, e.g. phone call. Those AEs should however, not be reported in the CRF.

Information required

For each AE, the investigator should provide the information requested on the appropriate eCRF pages. The investigator should determine the causal relationship to the study procedures.

If such abnormalities already pre-exist prior to study inclusion they will be considered as baseline conditions and should be collected in the eCRF only.

5.2 ASSESSMENT OF BIOMARKER(S)

This section describes the exploratory biomarkers which will be measured in the study.

For all biomarker endpoint, baseline is defined as the value at Visit 2; if not measured at Visit 2 then baseline is the value at Visit 1. All ophthalmologic examinations will be performed on in the study eye only, as described below.

Centrally collected ophthalmological data (microperimetry, color fundus photography, OCT/OCT-A) will be transferred from the CRC to the sponsor's database. The local measurement data will remain at the study sites as source documents.

Microperimetry

Microperimetry is a psychophysical technique allowing for a detailed assessment of function across specific areas of the retina such as the macula. Specific standardized patches of the retina are stimulated with points of light, and the test subject presses a button when he is able to perceive the light spot. In order to assess the light sensitivity at each test location, the stimulus intensity is lowered gradually. The fundus is monitored through an infrared camera and the fixation point is continuously tracked, thereby allowing for mapping the sensitivities of the test spots to the fundus and to images obtained with e.g. FAF imaging.

SS-OCT / SD-OCT-Angiography

The retinal layers and their thickness can be visualized and measured by SS-OCT (for direct comparison SD-OCT imaging will be performed). The assessment will be performed by a qualified person, and only specified OCT equipment will be used. OCT-A is a non-invasive imaging technique that provides high-resolution volumetric blood flow information without the use of dye. The assessment is also performed by a qualified person, and only specified device(s) will be used. OCT images will be sent to an independent CRC for evaluation. A detailed manual for OCT image acquisition and data transmission will be provided.

Visual Acuity measured by ETDRS letter charts

[figure not shown]
BCVA will be determined by using the ETDRS visual acuity chart starting at a test distance of 4 meters. The BCVA score is the number of letters read correctly by the patient. The assessment will be performed by a trained person under specified conditions regarding examination room and equipment.

FAF and Near Infrared imaging

[figure not shown]
FAF is an imaging technology for the morphological assessment of GA. The fluorescence signal predominantly originates from fluorescent material within RPE cells. In eyes with GA, distinctly dark areas are observed where the atrophy of RPE cells leaves an absence of fluorescent signal allowing for a quantification of the size of atrophic regions. Furthermore, FAF may support the prediction of the progression rate of GA via imaging the appearance of the hyperfluorescent junctional zone (i.e., the boundary between dead and surviving RPE regions, which is likely to represent RPE and/or photoreceptor cells which are more likely to become atrophic). Specifically, retinæ with junctional zones of the banded or diffuse type are more likely to progress than retinæ with focal junctional zones. Therefore, the type of the junctional zone appearance in the FAF can be utilized to define inclusion criteria for this clinical study.

Low Luminance Visual Acuity (LLVA)

To determine visual acuity under low luminance condition, the amount of light transmitted is reduced by neutral density filters placed over the eye to be tested, and the subject is asked to read the letters of a ETDRS visual acuity chart which normally illuminated. Because of the filter-reduced luminance, LLVA scores are lower than for BCVA (the magnitude of the difference between BCVA and LLVA is defined as Low Luminance Deficit (LLD)). LLVA measurements reveal visual function abnormalities not apparent by measuring standard BCVA alone and might be a more sensitive indicator for the risk of visual decline than assessing only standard BCVA.

5.2.1 Biobanking

6. INVESTIGATIONAL PLAN

6.1 VISIT SCHEDULE

All study visits should take place is pointed out in the [Flow Chart](#) and all patients are to adhere to the visit schedule as specified in the [Flow Chart](#).

If any visit has to be rescheduled, subsequent visits should follow the original visit date schedule.

6.2 DETAILS OF STUDY PROCEDURES AT SELECTED VISITS

Patients must sign Informed Consent before any study related procedures are performed.

Signing of the Informed Consent is not necessarily the start of the screening visit.

Once Visit 1 procedures are complete inclusion/exclusion criteria must be reviewed. If patient meets inclusion/exclusion criteria, patient should be contacted to schedule next visit.

If patient does not meet inclusion/exclusion criteria the patient must be recorded in CRFs as a screen failure.

6.2.1 Observation period

Assessments should be performed as mentioned in [Flow Chart](#), the respective protocol sections and in the imaging manual.

7. STATISTICAL METHODS AND DETERMINATION OF SAMPLE SIZE

7.1 STATISTICAL DESIGN - MODEL

The main objective of this longitudinal observational study is to investigate the use of microperimetry and SS-OCT in assessing the natural changes of retinal sensitivity and anatomy in patients with GA. In addition, changes in several other ophthalmologic measurements over time will be examined.

To this end, point estimates and confidence intervals (CIs) for the primary and secondary endpoints will be determined. Correlations between interesting pairs of outcome measures will be assessed.

7.2 NULL AND ALTERNATIVE HYPOTHESES

It is not planned to test any statistical hypotheses in a confirmatory sense. All statistical analyses are exploratory even if they use confirmatory methods.

7.3 PLANNED ANALYSES

All subjects entering the study will be included in the analyses. Protocol violations will be defined in TSAP. A per-protocol set will be defined accordingly thereafter.

7.3.1 Primary endpoint analyses

For each primary endpoint (see [section 2.1.2](#)), baseline is defined as the measurement obtained at Visit 2.

The following descriptive statistics will be calculated for the measurements related to the primary endpoints at each time point, as well as for the changes from baseline: N, arithmetic mean, Standard Deviation (SD), minimum, median, maximum, percentiles, arithmetic coefficient of variation.

Correlations (both Pearson and rank-based) of the changes from baseline of retinal sensitivity in the junctional zone and in the perilesional zone, respectively, of the largest atrophic loci as measured by microperimetry to the following endpoints will be estimated:

- Change from baseline in RPE layer thickness in the junctional zone and in the perilesional zone, respectively, as measured by SS-OCT and by SD-OCT
- Change from baseline in photoreceptor layer thickness in the junctional zone and in the perilesional zone, respectively, as measured by SS-OCT and by SD-OCT
- Changes from baseline in GA area as measured by FAF
- Change from baseline in the area of choriocapillaris flow deficits as measured via OCT-A at week 12, 24 and 48

Individual data as well as summary statistics will be visualised in respective graphical presentations, e.g. scatter plots or box-plots.

Correlations between the primary endpoints and continuous baseline characteristics will be investigated if necessary.

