	
• Change from baseline in photoreceptor layer thickness in the junctional zone and in the perilesional zone as measured by SS-OCT at week 24 and 48• Change from baseline in the GA area as measured by FAF at week 12, 24 and 48• Change in BCVA score as assessed by ETDRS chart at a starting distance of 4 m at week 12, 24 and 48• Change in LLVA score as assessed by ETDRS chart under low luminance conditions at a starting distance of 4 m at week 12, 24 and 48• Number of scotomatous points assessed by microperimetry at week 12, 24 and 48• Change from baseline in the area of choroidal non-perfusion as measured via OCT-A at week 12, 24 and 48
Safety criteria:	Adverse events
Statistical methods:	All endpoints will be evaluated descriptively.

FLOW CHART

Trial Periods	Screening	Observation Period			
Visit	1	2 (Baseline)	3	4	5
Weeks	-4 to -1		12	24	48
Time window for visits			±2 weeks	±2 weeks	±2 weeks
Informed consent	X				
In/exclusion criteria	X	X			
Demographics	X				
Medical history	X				
BCVA testing (starting at 4 m)	X	X	X	X	X
Low Luminance Visual Acuity		X	X	X	X
SD-OCT	X	X	X	X	X
SS-OCT with OCT-A	X	X	X	X	X
FAF and Near Infrared imaging	X	X	X	X	X
Microperimetry	X ¹⁾	X	X	X	X
Concomitant medication	X	X	X	X	X
Concurrent ocular procedures	X	X	X	X	X

- 1) Microperimetry examination to be executed twice with few minutes of resting
- 2) Do be performed only after Microperimetry testing has been done in order to avoid that the microperimetry is influenced by the light used for Color Photography.
- 3) Optional

TABLE OF CONTENTS

TITLE PAGE	1
CLINICAL TRIAL PROTOCOL SYNOPSIS	2
FLOW CHART	5
TABLE OF CONTENTS	6
ABBREVIATIONS	9
1. INTRODUCTION.....	10
1.1 MEDICAL BACKGROUND.....	10
1.2 RATIONALE FOR PERFORMING THE STUDY	10
2. TRIAL OBJECTIVES AND ENDPOINTS.....	11
2.1 MAIN OBJECTIVES, PRIMARY AND SECONDARY ENDPOINTS.....	11
2.1.1 Main objectives.....	11
2.1.2 Primary endpoints.....	11
2.1.3 Secondary endpoints	11
2.2 FURTHER OBJECTIVES AND FURTHER ENDPOINTS	11
2.2.1 Further objectives	11
2.2.2 Further endpoints	12
3. DESCRIPTION OF DESIGN AND TRIAL POPULATION.....	13
3.1 OVERALL STUDY DESIGN AND PLAN	13
3.2 SELECTION OF STUDY POPULATION.....	13
3.2.1 Main diagnosis for study entry	13
3.2.2 Inclusion criteria	13
3.2.3 Exclusion criteria	14
3.2.4 Withdrawal of patients from study participation	15
3.2.4.1 Withdrawal of consent for study participation.....	15
3.2.4.2 Discontinuation of the study by the sponsor	15
4. TREATMENTS.....	16

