7.7 DETERMINATION OF SAMPLE SIZE

The chosen number of 50 patients with GA is assumed to be sufficient for the purpose of investigating the distribution of the microperimetry measurements and their short-term changes in this patient population.

In particular, for this trial a precision (the half-width of the 95% CI) of 0.3 dB for the mean change from baseline in retinal sensitivity has been considered sufficient by the project team. [Table 7.5: 1](#) provides an overview of numbers needed for obtaining a 95% CI for the mean change from baseline in retinal sensitivity with a given half width with at least 90% probability, under various assumptions for the underlying SD. For example, assuming an SD of 0.9, the trial will need 47 patients in order to achieve two-sided 95% CIs for the given precision with a probability of 90%. For an SD of 0.7, the required sample size would be 31. Note that the SD for longitudinal changes from baseline of the retinal sensitivity in 8 patients with GA as seen in Wu et al. [[R17-1097](#)] was about 0.62.

Table 7.5: 1 Number of patients needed for obtaining a 95% CI for the mean change from baseline of retinal sensitivity with a given half width with at least 90% probability, for different SD values

Half-width of CI [dB]	Assumed SD			
	0.60	0.7	0.8	0.9
0.20	47	61	77	96
0.25	33	42	53	64
0.30	24	31	39	47

The calculation was performed as described by Julious [[R11-5230](#), Chapter 8] using R Version 3.3.2.

8. INFORMED CONSENT, TRIAL RECORDS, DATA PROTECTION, PUBLICATION POLICY, AND ADMINISTRATIVE STRUCTURE

The study will be carried out in compliance with the protocol and the ethical principles laid down in the Declaration of Helsinki.

Standard medical care (prophylactic, diagnostic and therapeutic procedures) remains the responsibility of the treating physician of the patient.

The BI transparency and publication policy can be found on the following web page: trials.boehringer-ingelheim.com. The rights of the investigator and of the sponsor with regard to publication of the results of this trial are described in the investigator contract. As a rule, no trial results should be published prior to finalization of the Clinical Trial Report (CTR). The certificate of insurance cover is made available to the investigator and the patients, and is stored in the Investigator Site File (ISF).

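### Baseline is the Visit 2 value alone although SS-OCT and microperimetry are also done at Visit 1; a two-session baseline would reduce, not remove, the measurement error in the change scores

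*Combined protocol and SAP*

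**What the plan says.** Section 7.3.1 states for each primary endpoint that "baseline is defined as the measurement obtained at Visit 2". Section 5.2, covering all biomarker endpoints, is slightly different: "baseline is defined as the value at Visit 2; if not measured at Visit 2 then baseline is the value at Visit 1". Neither section averages the visits or gives a reason for not doing so.

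The Flow Chart row "SS-OCT with OCT-A" is marked at Visits 1 to 5, and so is microperimetry. Footnote 1, attached to microperimetry at Visit 1 only, reads: "Microperimetry examination to be executed twice with few minutes of resting". Each enrolled eye should therefore have two SS-OCT sessions and three microperimetry examinations before follow-up starts. The Flow Chart places Visit 1 one to four weeks before baseline, and section 3.1 describes a "screening period of up to 28 days (Days -28 to -1") window.

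Apart from the substitution rule in 5.2, the only stated use of the Visit 1 microperimetry pair is exclusion criterion 3: "Mean sensitivity difference > 3 dB between the two microperimetry examinations in the screening visit".

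Section 7.7 bases the sample size on "a precision (the half-width of the 95% CI) of 0.3 dB for the mean change from baseline in retinal sensitivity", with the example "assuming an SD of 0.9, the trial will need 47 patients in order to achieve two-sided 95% CIs for the given precision" at 90% probability. Section 7.2 makes all analyses exploratory, and section 7.5 rules out imputation. The further-endpoint sections (2.2.2 and 7.3.3) are blank in the public text, and nothing is inferred from them.

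**The concern.** The study exists to find out how well these instruments track change, and its size rests entirely on the SD of a change score. Over 12 weeks, part of that SD may be test-retest error. The error in the one Visit 2 measurement enters the changes at weeks 12, 24 and 48 alike. It widens the intervals and pulls the planned sensitivity-structure correlations towards zero. A second baseline session has already been scheduled, so some of this error could be averaged out with no extra examination.

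The two baseline definitions also conflict. Because missing data are not imputed, a patient with Visit 1 but no Visit 2 measurement has a change score under 5.2 and none under 7.3.1.

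**Working it through.** **Inputs.** From section 7.7: target half-width w = 0.3 dB, SD of change 0.9, N = 50, 90% probability, and an external SD of about 0.62 from 8 patients. From the Flow Chart: two sessions, 1 to 4 weeks apart. Not in the documents: the share f of the variance of change that is measurement error. It is assumed to lie between 0.25 and 1.

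**Step 1: reproduce the plan's figure.** Find the smallest n with P(t(0.975, n−1)·S/√n ≤ w) ≥ 0.90, where (n−1)S²/SD² is chi-square on n−1 degrees of freedom. At SD 0.9 the probability is 0.887 for n = 46 and 0.910 for n = 47, so n = 47 as stated. All 12 cells of Table 7.5: 1 reproduce.

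**Step 2: precision with N = 50 as planned.** The half-width met with 90% probability is t(0.975, 49)·SD/√50·√(χ²(0.90, 49)/49) = 2.0096 × 0.9/7.071 × √(62.04/49) = 0.288 dB. This is inside 0.3 dB if all 50 are evaluable.

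**Step 3: effect of averaging.** Let each session have independent error variance s². With one baseline the error part of the variance of change is s² + s² = 2s². With two it is s² + s²/2 = 1.5s². The follow-up error is untouched. The variance of change is therefore multiplied by 1 − f/4, and the SD by √(1 − f/4).

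| f | SD multiplier | SD 0.9 becomes | n for 0.3 dB | Half-width at N = 50 (dB) |
|---|---|---|---|---|
| single baseline | 1 | 0.900 | 47 | 0.288 |
| 0.25 | 0.968 | 0.871 | 45 | 0.279 |
| 0.50 | 0.935 | 0.842 | 42 | 0.269 |
| 0.75 | 0.901 | 0.811 | 40 | 0.259 |
| 1 | 0.866 | 0.779 | 37 | 0.249 |

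At SD 0.62 the number needed falls from 26 to between 24 and 21. No SD is given for SS-OCT thickness, so only the multiplier column applies there.

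**Step 4: correlations.** If both change scores have the same f, both use averaged baselines and their errors are independent of each other, the observed correlation is multiplied by 1/(1 − f/4): 1.07, 1.14 and 1.23 for f = 0.25, 0.5 and 0.75. At f = 1 there is no true variation in change to correlate. Where only the microperimetry side is averaged, the factor is the square root: 1.03, 1.07 and 1.11.

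**Step 5: cost of a shift between visits.** If Visit 1 differs from Visit 2 by d on average, for example through practice, the averaged baseline moves the mean change by d/2. Mean squared error becomes worse once (d/2)² > (SD²/N)(f/4), that is |d| > SD·√(f/N). At SD 0.9 and N = 50 this is 0.9·√(0.25/50) = 0.06 dB to 0.9·√(1/50) = 0.13 dB. At SD 0.62 it is 0.04 to 0.09 dB.

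**Step 6: timing.** Averaging over a gap of 1 to 4 weeks moves the baseline back by 0.5 to 2 weeks, which lengthens a 12-week interval by 0.5/12 = 4% to 2/12 = 17%.

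**The case against.** Three stronger readings are tempting, and the documents support none of them.

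- *A reader might infer that averaging eliminates the error.* It halves the baseline part at most, which is at most 25% of the variance of change.
- *A reader might infer that the sample size falls short.* The planning SD is for the change score itself, so single-baseline error is already in it. The 3-patient margin (50 − 47) belongs to the most cautious column of the table. At SD 0.8, 0.7 and 0.62 the plan needs 39, 31 and 26, leaving 11, 19 and 24.
- *A reader might infer that the averaged value should replace Visit 2 throughout.* For the microperimetry mean change this is a trade-off. Step 5 shows that a very small shift cancels the gain. The second Visit 1 examination comes minutes after another, and neither Visit 2 nor any follow-up visit carries that footnote, so Visit 2 is the closer match to follow-up. Practice or fatigue at Visit 1 cannot be excluded, and section 3.1 permits rescreening up to twice, so prior exposure may differ between patients.

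It is also fair to say that f is unknown, that it should fall by week 48 as true change accumulates, that correlated session errors would shrink the gain, and that the single-baseline SD is itself a useful result of this study.

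These points limit the change but do not dispose of it. SS-OCT thickness, which supplies two of the three primary endpoints, needs no patient response and so has no practice effect. A shift that is the same for all patients leaves the SD, the interval width and the correlations unchanged; only the mean moves. The 3 dB exclusion selects on disagreement within the pair, not on level, so it gives no obvious directional bias.

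**Conclusion.** This is a low-cost gain in efficiency. It corrects no error in the sample size, and no stated target is missed. Under independent session errors and f from 0.25 to 1, a two-session baseline lowers the SD of change by 3% to 13%, with less attenuation of the planned correlations. The gain is smaller if f is lower or session errors are correlated. The case is good for SS-OCT thickness and for the correlations. For the microperimetry mean change it supports a second result shown beside the Visit 2 one, so the smaller sample sizes in the table describe that second result and not the main estimate. The disagreement between sections 5.2 and 7.3.1 rests on no assumption and needs settling in any case.

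**What to change.** 1. Reconcile sections 5.2 and 7.3.1 into one baseline definition, stating whether Visit 1 may stand in when Visit 2 is missing.
2. Define the SS-OCT layer-thickness baseline as the mean of the Visit 1 and Visit 2 values, or the available one if the other is missing.
3. For the change-score correlations, use as microperimetry baseline the mean of the second Visit 1 examination and the Visit 2 examination. State which Visit 1 counts for a rescreened patient.
4. For the microperimetry mean change, keep Visit 2 as the main baseline. Report the averaged-baseline result beside it, with the observed Visit 1 to Visit 2 shift.
5. Keep a Visit 2-only summary for all endpoints, so that the variability of a single-baseline design is still on record.

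The cost is some analysis-plan wording and one derived variable, with no added examination. The drawback is that the averaged baseline sits 0.5 to 2 weeks earlier and by a different amount for each patient; the retained Visit 2-only summary lets the reader judge its effect.
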